9.8 Safety Analysis

All safety analyses will be performed on the safety population. Full details will be included in the SAP. Planned data presentations and analyses include the following:

Adverse events will be coded using MedDRA. Adverse event listings will include the verbatim term and the MedDRA preferred term. Treatment-emergent adverse events will be summarized by system organ class and preferred term. Treatment-emergent adverse events leading to death or to discontinuation from treatment, treatment-emergent adverse events (TEAEs) classified as National Cancer Institute (NCI) Common Terminology Criteria for Adverse Events (CTCAE) (version 4.03) all grades or grade 3/4 TEAEs, related to investigational product, and serious TEAEs will be summarized separately.

Clinical laboratory results will be summarized descriptively by treatment group. Clinically significant hematologic and non-hematologic laboratory abnormalities will be listed and summarized according to the NCI CTCAE (version 4.03) by treatment group.

Physical examination data and vital sign measurements, including body weight, will be listed for each subject at each visit. Descriptive statistics for vital signs, both observed values and changes from baseline, will be summarized by treatment group.

9.9 Interim Analysis

Two interim analyses are planned. The first interim analysis (IA) is for futility and the second IA is for efficacy.

For the first IA, the primary efficacy variable, RBC transfusion independence (12 weeks with a concurrent hemoglobin increase), will be compared between the two treatment arms using the CMH test at approximately 30% information (when approximately 105 subjects have completed 24 weeks of treatment, or discontinued before reaching 24 weeks of treatment). A non-binding β -spending function of the O'Brien-Fleming type will be used to control the Type II error rate with overall one-sided $\beta = 0.10$.

At the first interim analysis, CMH statistic will be calculated and compared with the futility boundary. If the value of the CMH statistics is below the futility boundary, a recommendation to stop the study due to futility can be considered.

Equivalently, the p-value for the one-sided CMH test will be calculated and a recommendation to terminate will be made if the p-value is greater than the futility boundary. The table below gives the nominal p-value for rejecting the alternative hypothesis corresponding to the O'Brien-Fleming boundary. (The interim bound is approximate and will be re-calculated based on the amount of information available when the interim analysis is actually performed.)

Table 8: Futility Interim Boundaries for the first IA

Analysis	Futility Bound (odds ratio)	Reject Alternative Hypothesis if p greater than
Interim (30%)	0.632	0.844

Note: Nominal p-values for futility computed using the program East Version 6.4 (Cytel Statistical Software Company).

Thus, if at the first interim analysis, the p-value is greater than 0.844, then the DMC could consider stopping the trial due to futility.

A second interim analysis is planned to test the superiority of the primary endpoint at about 85% of the information (when approximately 300 subjects have completed 24 weeks of treatment or discontinued before reaching 24 weeks of treatment).

At the second interim analysis, the p-value from the one-sided CMH test for the primary endpoint will be calculated. If the one-sided p-value is less than or equal to 0.015, DMC could recommend that luspatercept is superior to epoetin alfa in terms of the primary endpoint. If the one-sided p-value is greater than 0.015, the study will continue as planned and the p-value from the one-sided CMH test at the final analysis will be compared against the significance level 0.021. The Lan-DeMets spending function of the O'Brien-Fleming type will be used to control the overall one-sided alpha level at 0.025.

At the time of second interim analysis, gate-keeping method will be used to control the Type I error rate for the following secondary endpoints in the order of:

- HI-E response (Week 1 to 24)
- RBC-TI for 24 weeks (Week 1 to 24)
- RBC-TI \geq 12 weeks (Week 1 to 24)

After the result from the primary efficacy endpoint shows statistical significance at the level of 0.015, RBC-TI for 24 weeks in Week 1 to 24 will be tested for significance at a one-sided significance level of 0.015 only if both the primary endpoint and HI-E response in Week 1 to 24 are significant at the one-sided significance level of 0.015. RBC-TI \geq 12 weeks in Week 1 to 24 will be tested for significance only if the results for primary endpoint, HI-E in Week 1 to 24, and RBC-TI for 24 weeks in Week 1 to 24 are all significant at the one-sided significance level of 0.015. The testing procedure above will be implemented strictly in order to control the overall one-sided Type I error rate of 0.015 at the interim analysis due to multiplicity.

Other secondary endpoints will be analyzed without employing methods for controlling the Type I error rate. Any statistically significant treatment effect on these secondary endpoints cannot be interpreted as confirmatory, but rather informative.

The table below summarizes alpha spent at each analysis. Note that the actual alpha level used at the second interim analysis will be determined based on the actual information fraction (percent of subjects who have completed 24 weeks of treatment or discontinued before reaching 24 weeks of treatment) at the second interim analysis.

Table 9: Summary of Alpha Spending

Analysis	Enrollment	One-sided alpha	Endpoint Assessment
Futility Interim	30% information for primary endpoint (105 subjects)	N/A	Efficacy not tested
Superiority Interim	85% information for primary endpoint (300 subjects)	0.015	Testing in order of: Primary endpoint HI-E response (Week 1 to 24) RBC-TI for 24 weeks (Week 1 to 24) RBC-TI \geq 12 weeks (Week 1 to 24)
Superiority Final	100% information for primary endpoint (350 subjects)	0.021	Testing in order of: Primary endpoint HI-E response (Week 1 to 24) RBC-TI for 24 weeks (Week 1 to 24) RBC-TI \geq 12 weeks (Week 1 to 24)

Abbreviations: HI-E = Hematologic improvement – erythroid response; N/A = not applicable; RBC-TI = Red blood cell transfusion independence

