A total sample size of approximately 350 subjects (175 subjects in the experimental arm [luspatercept (ACE-536)], 175 subjects in the control arm [epoetin alfa]) will have 90% power to detect the difference between a red blood cell transfusion independence (RBC-TI) for any 12-week period associated with a concurrent mean hemoglobin increase of 1.5 g/dL response rate of 36% in the experimental arm (luspatercept [ACE-536]) and a response rate of 20 % in the control arm (epoetin alfa), with one interim analysis on futility only when about 105 subjects have completed 24 weeks of treatment, or discontinued before reaching 24 weeks of treatment (30% information for the primary endpoint). The sample size calculation is based on one-sided alpha of 0.025, test statistics on odds ratio of proportions.

The primary efficacy analysis will be the comparison of the response rates in the two treatment arms in the intent-to-treat (ITT) population. The primary efficacy endpoint is defined as the absence of any RBC transfusion of ≥ 12 weeks with a mean hemoglobin increase ≥ 1.5 g/dL during the same time period over the first 24 weeks from baseline (Week 1 through Week 24) during the Treatment Period.

The Cochran–Mantel–Haenszel (CMH) test will be used to compare the response rates from treatment group and control group with randomization factors as strata. Kaplan–Meier methods will be used to characterize the duration of response and survival.

The first interim analysis to assess futility will be performed when approximately 105 subjects have completed 24 weeks of treatment or discontinued before reaching 24 weeks of treatment (30% information for primary endpoint).

A second interim analysis for superiority will be performed when approximately 300 subjects have completed 24 weeks of treatment or discontinued before reaching 24 weeks of treatment (85% information for primary endpoint).

The addition of the second interim analysis does not alter the original sample size calculation. The study power remains at 90% for the final analysis with 350 subjects. The Lan-DeMets spending

function of the O'Brien-Fleming type will be used to control the overall one-sided Type I error rate at 0.025. The following significance level will be used:

- Superiority interim analysis (85% information for primary endpoint): one-sided alpha of 0.015
- Final analysis (100% information for primary endpoint): one-sided alpha of 0.021

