9.7 Efficacy Analysis

9.7.1 Primary Efficacy Analysis

The primary efficacy analysis will be the comparison of the response rates in the two treatment arms in the ITT population. The primary efficacy endpoint of RBC transfusion independence for 12 weeks with an associated concurrent mean increase of ≥ 1.5 g/dL Hgb increase, is defined as the absence of any RBC transfusion for any 12-week period from Week 1 to the end of Week 24 associated with a concurrent mean increase of hemoglobin of at least ≥ 1.5 g/dL compared to baseline.

For the primary efficacy endpoint, the response rate will be calculated using the number of responders divided by number of subjects in the ITT population (responders plus non-responders). The response rates of the subjects who were randomized to luspatercept and the epoetin alfa arm will be calculated. In the primary efficacy analysis, the statistical hypothesis is

$$H_0 : P_1 \leq P_2$$

$$H_a : P_1 > P_2$$

where P_1 denotes the true response rate in the luspatercept group, and P_2 denotes the true response rate in the epoetin alfa group. The number and percentage of subjects in the ITT population who achieve the response will be presented by treatment group. The Cochran–Mantel–Haenszel (CMH) test will be used to test the difference between the two response rates with randomization factors as strata. The one-sided significance level at the final analysis will be 0.021 with one planned interim analysis for superiority.

Additional details will be outlined in the SAP.

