9.7.2 Secondary Efficacy Analyses

The secondary efficacy endpoints will be analyzed and reported at the time of the analysis of the primary efficacy endpoints.

Secondary endpoints will be analyzed descriptively, unless otherwise specified, and will be based on the ITT population. Kaplan-Meier methods will be used to estimate curves for time to event secondary variables. Count, percentages, and 95% confidence interval will be used to describe categorical secondary variables.

Gate-keeping method will be used to control the overall Type I error rate for the following secondary endpoints in the order of:

- HI-E response (Week 1 to 24)
- RBC-TI for 24 weeks (Week 1 to 24)
- RBC-TI ≥ 12 weeks (Week 1 to 24)

After the result from the primary efficacy endpoint shows statistical significance, RBC-TI for 24 weeks in Week 1 to 24 will be tested for significance at the one-sided significance level of 0.021 only if both primary endpoint and HI-E response in Week 1 to 24 are significant. RBC-TI ≥ 12 weeks in Week 1 to 24 will be tested for significance at the one-sided significance level of

0.021 only if the results for primary endpoint, HI-E in Week 1 to 24, and RBC-TI for 24 weeks in Week 1 to 24 are all significant. The testing procedure above will be implemented strictly in order to control the overall one-sided Type I error rate of 0.025 due to multiplicity.

Other secondary endpoints will be analyzed without employing methods for controlling the type one error rate. Any statistically significant treatment effect on these secondary endpoints cannot be interpreted as confirmatory, but rather informative.

RBC transfusion independence (RBC-TI) for 24 weeks is defined as the absence of any RBC transfusion from Week 1 to the end of Week 24. Subjects discontinued from the Treatment Phase prior to finishing Week 24 will be counted as non-responders.

Mean hemoglobin change over 24 weeks is defined as the mean hemoglobin change over the 24-week period of Week 1 through Week 24 compared to baseline

Hematologic improvement – erythroid response (HI-E) per IWG (Cheson, 2006) is defined as proportion of subjects meeting HI-E criteria sustained over any consecutive 56-day period over the first 24 weeks from Week 1. Subjects discontinued from the Treatment Period without achieving HI-E will be counted as non-responders.

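### The interim level follows the actual information, but the final level is fixed at 0.021 (0.0207 rounded up), so overall one-sided error slightly exceeds 0.025 at the planned look or later

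*Combined protocol and SAP*

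**What the plan says.** Section 9.9 plans a non-binding futility look at about 30% information and a superiority look at about 85%, given as approximately 300 of 350 subjects. On overall error it states: "The Lan-DeMets spending function of the O'Brien-Fleming type will be used to control the overall one-sided alpha level at 0.025".

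The three boundaries are treated differently:

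- **Futility bound (Section 9.9, above Table 8):** "The interim bound is approximate and will be re-calculated based on the amount of information available when the interim analysis is actually performed".
- **Interim efficacy level (Section 9.9, note before Table 9):** "Note that the actual alpha level used at the second interim analysis will be determined based on the actual information fraction". The planned value is 0.015.
- **Final level:** no statement that it will be recalculated. Section 9.9 says "the p-value from the one-sided CMH test at the final analysis will be compared against the significance level 0.021", Section 9.7.1 says "The one-sided significance level at the final analysis will be 0.021 with one planned interim analysis for superiority", and the Statistical Methods part of the Protocol Summary says "Final analysis (100% information for primary endpoint): one-sided alpha of 0.021". Table 9 repeats 0.021.

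Section 9.7.2 carries the same figure into the gated secondary endpoints. RBC-TI for 24 weeks "will be tested for significance at the one-sided significance level of 0.021 only if both primary endpoint and HI-E response" is met, and RBC-TI of at least 12 weeks follows at the same level. The section adds: "The testing procedure above will be implemented strictly in order to control the overall one-sided Type I error rate of 0.025 due to multiplicity".

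**The concern.** In a two-look spending design the final critical value is whatever remains after the interim, given the alpha spent there and the correlation between the looks. If the interim level moves with the information fraction, the final level has to move too. The plan adapts one half of a linked pair and freezes the other. The frozen value is also a critical level rounded upward, which is the anti-conservative direction.

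What is at stake is a narrow band of final p-values. After an interim at 300/350, a final p-value between 0.0206 and 0.0210 would be declared significant under the written rule although the spending function does not allow it. The same band applies to the gated secondary endpoints. The plan's claim to control 0.025 would then not be true of the procedure that it describes.

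**Working it through.** **Inputs.** Overall one-sided alpha 0.025 with Lan-DeMets O'Brien-Fleming spending (9.9). Superiority look at about 85%, or 300/350 = 85.7% (9.9, Table 9). Levels 0.015 and 0.021 (Table 9). The futility look is non-binding, so it returns no alpha (9.9). Design rates are 36% versus 20% with 175 per arm (9.3).

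**Formulas.** With *t* the information fraction at the superiority look:

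- Alpha spent at the interim: a(t) = 2[1 − Φ(z/√t)], with z = Φ⁻¹(1 − 0.0125) = 2.2414.
- Final critical value c₂: solves 1 − P(Z₁ < c₁, Z₂ < c₂) = 0.025, where c₁ = Φ⁻¹(1 − a(t)) and corr(Z₁, Z₂) = √t.

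**Reproducing the plan's figures (t = 0.85).** √0.85 = 0.9220 and 2.2414/0.9220 = 2.4311, so a = 0.01505 and c₁ = 2.169. Solving gives c₂ = 2.039, a final level of 0.02072. To three decimals these are the printed 0.015 and 0.021. The classical O'Brien-Fleming boundary would give 0.0140 and 0.0214, so the printed pair is indeed the spending-function pair.

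**Applying the written rule at other looks.** The fourth column recomputes the interim level and keeps 0.021 at the end. The last column holds both printed values fixed.

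| Information at look | Interim level | Exact final level | Overall error: interim recomputed, final 0.021 | Overall error: 0.015 and 0.021 both fixed |
|---|---|---|---|---|
| 80% | 0.01221 | 0.02144 | 0.02464 | 0.02617 |
| 83% | 0.01388 | 0.02101 | 0.02499 | 0.02560 |
| 85% | 0.01505 | 0.02072 | 0.02522 | 0.02519 |
| 300/350 | 0.01548 | 0.02062 | 0.02529 | 0.02504 |
| 90% | 0.01814 | 0.02004 | 0.02566 | 0.02404 |
| 95% | 0.02147 | 0.01958 | 0.02578 | 0.02263 |

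Under the written rule the error crosses 0.025 at t = 0.8305 (0.8305 × 350 ≈ 290 subjects). It peaks at 0.0258 near 94% and falls back to 0.025 only beyond about 99.4%. Both planned descriptions of the look, 85% and 300/350, lie above the crossover.

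**Four decimals alone do not cure it.** The pair 0.0150/0.0207 totals 0.02496 at 85%. If the look falls at 300/350 and the interim level is recomputed to 0.01548, a fixed 0.0207 gives 0.02506. The final level has to be solved, not just printed more finely.

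**Power.** The log odds ratio is ln[(0.36/0.64)/(0.20/0.80)] = 0.8109. Its standard error is √[1/(175 × 0.36 × 0.64) + 1/(175 × 0.20 × 0.80)] = 0.2460, so the drift is 3.296. With a look at 300/350, two-look power is 0.9034 with the exact final level (0.01548/0.02062) and 0.9044 with 0.021.

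**The case against.** The strongest reply is that the plan already states the governing rule. The sentence that invokes the spending function comes straight after the 0.021 sentence in Section 9.9, the timing is described as approximate, and a statistician could read 0.021 as the planned value for that timing. On that reading both levels are recomputed and the error is 0.025. The reading is possible, but the text never states it. It gives explicit recalculation language for the other two bounds and compares the final p-value directly with 0.021.

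Second, the larger figures depend on recomputing the interim level while freezing the final one. That is correct. If both printed levels were held, the excess would disappear for looks after about 85.9%. But the note before Table 9 says the interim level will be re-determined, and the fixed pair still exceeds 0.025 at the planned look (0.02519 at 85%, 0.02504 at 300/350).

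Third, Section 9.7.1 defers further detail to an SAP, and the supplied text contains no separate SAP section. A rule there cannot be excluded. It would, however, have to depart from a level that the protocol states as fixed.

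Fourth, the excess is within the approximation error of the test. Exact binomial enumeration of an unstratified pooled test (150 then 175 per arm, null rates 20% to 36%) gives a true size between about 0.025 and 0.0256 under the written rule. This limits how literally the fourth decimal should be taken. It does not reverse the direction, since most of those values are above 0.025.

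Two supporting details carry little weight: the futility bound has no bearing on alpha, and the word about strict implementation in 9.7.2 refers to the testing order.

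**Conclusion.** The concern holds. The printed levels are correct to three decimals at 85% information, but used as the plan directs they do not deliver the stated 0.025. The excess is 0.0002 to 0.0003 at the planned look, where it is a rounding effect. It is at most 0.0008 for a later look, where it comes from the missing rule for the final level. A look at about 83% or earlier gives no excess.

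These figures assume that the interim level is recomputed and the final level is not, that the CMH statistic is asymptotically normal with independent increments, that information is proportional to subjects evaluated, and that the final analysis takes place at full information. The effect is small and would matter only for a final p-value in a narrow band. It should still be corrected, because it concerns a confirmatory threshold and the correction costs almost nothing.

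**What to change.** In the Protocol Summary, Sections 9.7.1, 9.7.2 and 9.9, and Table 9:

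1. Label 0.015 and 0.021 as planned, approximate values.
2. State that the final level will be solved from the spending function, using the alpha actually spent at the superiority interim and the actual information at both looks, and that it will be rounded down.
3. Give the planned pair to four decimals as a consistent pair: 0.0150 and 0.0207 at 85% information, totalling 0.02496.
4. Apply the same recomputed final level to the gated secondary endpoints.

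The cost is wording only. Sample size and timing do not change. The final threshold becomes marginally stricter at the planned look, and two-look power moves from 90.4% to 90.3% under the design assumptions.

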9.10 Other Topics

9.10.1 Health-related Quality-of-life Assessment

The effect of luspatercept and epoetin alfa on patients' HRQoL based on EORTC QLQ-C30, FACT-An, QUALMS-P and the Patient Treatment Satisfaction Survey will be assessed. The intent is to summarize the descriptive statistics of observed score at each visit and change from baseline at each post-baseline visit for all domains of the QLQ-C30 and FACT-An, QUALMS-P for each treatment group. Within-treatment and between-treatment differences will be examined using a 1-sample, 2-sided t-test and a pooled 2-sample, 2-sided t-test, respectively. However, these t-tests will be descriptive (ie, non-inferential) in nature.

In addition, the least square (LS) mean (95% confidence interval [CI] and p-value) for change from baseline at each post-baseline visit for all domains within each treatment group, and the difference in the LS means (95% CI, p-value) between treatment groups at each post-baseline visit, will be

estimated using the analysis of covariance (ANCOVA) model adjusting for baseline domain scores and stratification factors (ie, transfusion burden, RS status and sEPO level) where appropriate. Various schemes will be assessed for missing data imputation. Full details will be included in an HRQoL SAP.

9.10.2 Healthcare Resource Utilization

Characterization of certain medical resource utilization among subjects treated with luspatercept as compared to subjects receiving epoetin alfa. Examples of relevant healthcare resource utilization include hospitalizations, prior concomitant therapies and surgeries, as well as RBC transfusion utilization. Data for the analysis of healthcare resource utilization will be sourced both from specific report forms or through routine study data collection.

Full details will be included in the SAP.

9.10.3 Pharmacokinetic Analysis

Population PK analysis will be performed using nonlinear mixed effect modeling. Concentration data obtained from this study and other studies may be combined to develop a population PK model that describes the PK exposure data and the associated variability. Subject-specific factors (demographics, baseline characteristics, markers for organ function, ADA against luspatercept, etc.) will be explored as covariates for their potential to influence luspatercept PK parameters. Empiric individual Bayesian estimates of PK parameters will be generated using the final population PK model and appropriate measures of luspatercept exposure (area under the concentration-time curve [AUC], maximum plasma concentration of drug [C_{max}], or other exposure metrics of interest) will be computed for each subject. The relationship between serum luspatercept exposure and the primary efficacy endpoint, AEs of interest, or other selected secondary endpoints will be explored as appropriate.

Full details will be included in the PK/Pharmacodynamic (PD) Data Analysis Plan.

